Statistical analysis plan. Comparisons of clinical and demographic data between groups at baseline will be performed by the appropriate statistical test (for continuous variables, t-test for normally distributed data and Wilcoxon test for non-normal data; for categorical variables, chi-square test or Fisher's exact test). These comparisons will be performed at baseline only to assess adequacy of randomization. Comparisons between groups for cardiopulmonary exercise test, muscle biopsy, energy expenditure, cognitive function, and other functional measures before and after the study period will be performed by multivariate ANOVA; post-hoc comparisons will be made using the Bonferroni method. To analyze continuous variables measured at three or more time points we will use linear mixed effects regression (114). To explore the relationships between a given outcome and other variables, we will use multiple regression techniques. Since the reliability of a fitted regression model may be reduced if too many predictors are used (114), we will limit the number of predictors to four variables in each model ($\leq 1/10$ of the total). For the primary outcome, change in peak VO_2 , the specific independent variables in the model will include exercise compliance (average energy expended in kcals/week), change in muscle strength, and change in muscle mass. Missing data will be managed using the multiple imputation method which is preferable to older methods and described in detail by Schafer & Olsen (1999).

For Specific Aim 2 (effect of acute and chronic exercise on muscle wasting), we will employ a linear model, using period (baseline vs. 4 months) and treatment (exercise training vs. usual care) as independent variables along with their interaction (Bonferroni method). The intention to treat principal will be applied for all analyses.

Timeline. We anticipate that we will recruit ≈ 15 MHD subjects/year during the 4 years of the study. We expect that it will take four years to complete the study, with much of the final year dedicated to completing sample processing and data analysis. We do not expect much delay in getting started as there is an established exercise research program at our facility. In addition, the techniques for biopsying muscle as well as measuring muscle structure and cellular biology are established in the PI's ([name]) research laboratory. Finally, both the Satellite Healthcare Dialysis research group ([name]) and [name] group (Stanford University) have vast experience in recruiting and performing clinical trials in MHD patients. *A study Timeline of Project Tasks is presented in Appendix I.*

Plan for Dissemination. Dissemination will be a major focus of year 4. We believe the results of this study will lend themselves well to presentations at the VA RR&D meeting, American Society of Nephrology, and a number of rehabilitation meetings (AACVPR, ACSM). The Co-PIs will devote efforts during years 3 and 4 to abstract presentations and manuscript preparation. We anticipate that there will be results on functional and psychosocial outcomes that will be appropriate for publication in the Journal of Rehabilitation Research and Development, Journal of Cardiopulmonary Rehabilitation and Prevention, and Archives of Physical Medicine and Rehabilitation. Physiological results will be appropriate for the Journal of Applied Physiology and Nephrology journals, including Journal of the American Society of Nephrology, American Journal of Kidney Diseases, and others.

PRELIMINARY STUDIES

Exercise training studies. The Co-PI ([name]) and one of the Co-Investigators on the current proposal ([name]) have previously conducted a 3-year NIH-funded Specialized Center of Research (SCOR) project of exercise training in patients with cardiovascular disease (115; 116), and are currently conducting an NIH Specialized Center of Clinically-Oriented Research (SCCOR) project on the effects of exercise therapy in patients with abdominal aortic aneurism disease (87; 93). The proposed project will use existing exercise testing and training facilities at the VA Palo Alto Medical Center, and methods similar to the current NIH SCCOR project will be used in the current proposal.

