For recruitment we will draw on a large patient population within 30-40 miles of the VA Palo Alto Health Care System (VAPAHCS) with travel reimbursement provided. *For example, the nearby Satellite Healthcare Centers have agreed to actively support the identification and recruitment of subjects, with their Chief Medical Officer, [name], serving as a significant contributor to this study. They operate 30 stand-alone dialysis centers within a 40 mile radius the VA Hospital in Palo Alto. These centers treat a total of 5,000 dialysis patients, with approximately 25% of these patients on home dialysis. At any given time, approximately 2% of their total patient population is enrolled in a clinical trial. There are 6 Satellite Healthcare clinics within 10 miles of the VA Hospital in Palo Alto, which provide MHD services to roughly 1,000 patients; these clinics will be a primary source of patients for the study.* At Santa Clara Valley Medical Center, a Stanford affiliate, \approx 300 patients are treated with MHD and this facility has agreed to refer study subjects. Smaller dialysis clinics such as VAPAHCS ([name]), Stanford Medical Center ([name]) and community nephrologists (letters attached) will also serve as resources. Combined, these resources provide a pool of \approx 2,000 subjects in close proximity to our center. From prior experience, \approx 5% of subjects will meet inclusion criteria and agree to participate. This will provide an adequate enrollment pool. While we expect the recruitment of subjects to reflect the distribution of women and minorities in our area, a concerted effort will be made to recruit and include them in the study.

Study population and inclusion/exclusion criteria: Males and females aged 65-80 years undergoing MHD for at least three months and without other active/uncontrolled disease will be studied. Exercise and usual care groups will be *matched by age, body mass index (BMI), MHD duration, and protein intake* using a stratified randomization approach.

Inclusion criteria. MHD subjects with impaired exercise capacity and function will be considered for the study. Subjects will be required to be in the peak VO_2 range of 10 to 20 ml/kg/min, equivalent to moderate functional impairment in patients with heart failure (88; 89). Subjects will be required to have dialysis treatment for >3 months with an average $Kt/V \geq 1.2$, and be able to perform exercise safely. Racial

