Group Assignment. After screening and baseline testing, an independent third party investigator ([name], letter attached) will *match MHD subjects on age, body mass index (BMI), MHD duration, and protein intake*, and assign them randomly to the exercise or usual care study groups. At the end of 12 weeks of study this investigator will assign half of the subjects in each group to receive a blinded nutritional supplement (high calorie whey or placebo). The blind will be broken on completion of the study.

Dietary Control. Prior to entry into the study the subjects will be encouraged to consume 1.2 g protein/kg/day, per Kidney Disease Outcomes Quality Initiative (KDOQI) recommendations (92) and advised to maintain a steady intake. However, we realize that the recommended intake may not be achieved in some subjects. In order to adjust for variation in protein intake we will measure the subject's protein intake on 3 occasions during the month prior to entry into the study. Then when assigning subjects to the study groups, measured protein intake will be taken into account by the third part study assigner, so that the protein intake in the 2 study groups will be similar. Protein intake will be monitored by three-day dietary records and the normalized protein equivalent of nitrogen appearance (nPNA), a reflection of protein intake in stable conditions. nPNA is calculated from the urea generation rate by means of kinetic modeling using measurements of pre- and post-dialysis urea levels plus any urea lost in the urine in patients with residual renal function. After entry into the study nPNA is calculated weekly for the first two study weeks, then monthly. During the study period, there will be regular bi-weekly follow up counseling by a dietitian in an effort to ensure that both groups meet target dietary protein intakes

Safety Measures. Before screening, subjects will be informed of the nature of the study and the procedures to be performed, and will sign an approved consent form. Measures to monitor and ensure safety include a screening ECG, maximal exercise test, and medical approval (see screening). The cardiovascular exercise lab has extensive experience in conducting clinical studies and has a staff of experienced personnel. We do not expect any long-term side effects from the proposed interventions. The exercise program is well balanced and varied with aspects of strength and aerobic training. Subjects will

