Since this is a pilot sub-study carried out with a limited number of subjects after completion of the main 12 week study, we have adopted a unilateral exercise protocol in which the resting contralateral limb serves as a control. This protocol will allow us to gain considerable insight into the salutary molecular processes activated by exercise in ESRD subjects and to test whether these processes can be enhanced by provision of a leucine-rich supplement. In brief, two to three days after completing the primary 12-week study, subjects from both the exercise and usual care groups will be studied in which one limb is exercised for 15 minutes, after which the vastus lateralis muscles of both the exercised and the contralateral resting limb will be biopsied. *Half the subjects in each of these 2 main groups (12 subjects from each group) will be matched by BMI and age and randomized to either a placebo mixture or a high calorie nutrient supplement.* The nutrient supplement will consist of a high-calorie leucine-rich protein (whey protein) given at the start and end of the exercise session. The study consists of the following 4 groups, each undergoing acute, unilateral exercise:

- Group 1.** Regular exercise group plus placebo
- Group 2.** Regular exercise group plus nutrient supplement
- Group 3.** Usual care group plus placebo
- Group 4.** Usual care group plus nutrient supplement

An outline of the experimental protocol is illustrated in Figure 2, and a detailed protocol follows.

[figure not shown]
Figure 2. Acute Exercise, Muscle Biopsy, and Nutrient Supplement Protocol for Specific Aim 2

Biopsies will be obtained from the dominant limb after acute exercise and from the non-dominant limb following rest. A *single* biopsy of each limb will be taken from each subject. Tissue taken from the biopsies will undergo molecular analysis to answer the following questions:

[figure not shown]

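### Allocation method is loosely specified, and four-factor stratification suits 60 sequential entrants poorly; name one concealed, rule-based procedure

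*Combined protocol and SAP*

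**What the plan says.** Main allocation, in three places:

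- *Study population and inclusion/exclusion criteria*: the two groups are to be alike in age, BMI, time on MHD and protein intake, "using a stratified randomization approach".
- *Group Assignment*: after screening and baseline testing, an independent third party will "match MHD subjects on age, body mass index (BMI), MHD duration, and protein intake". The allocation that follows is stated to be random: the same party is to "assign them randomly to the exercise or usual care study groups".
- *Dietary Control*: "measured protein intake will be taken into account by the third part study assigner", with the aim that average intake comes out similar in the two groups.

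Supplement allocation, in two places:

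- *Group Assignment*: the same third party assigns half of each group to blinded whey or placebo at the end of the 12 weeks. Neither randomisation nor matching is mentioned.
- *B. Approach to Specific Aim 2*: the subjects "will be matched by BMI and age and randomized to either a placebo mixture or a high calorie nutrient supplement".

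The *Timeline* expects about "15 MHD subjects/year during the 4 years of the study", so subjects enter one at a time. The sample size rests on an unpaired two-group t-test, and the *Statistical analysis plan* has no pair or stratum term. Factor cut-points, block sizes, a pairing rule, an algorithm, the source of the random sequence and a concealment step are all absent from the supplied text.

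**The concern.** Someone charged with running this allocation could not do so from the text. Matching, stratified randomisation and taking a factor into account are different operations unless a rule ties them together, and none is given.

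Two things are at stake. The first is covariate balance: stratifying on four factors splits a 60-subject trial into cells so small that most blocks are never filled, and unfilled blocks do not balance. The second is selection bias. Exercise against usual care cannot be masked from subjects, and eligibility includes judgements, such as the exclusion for doubtful motivation under *Exercise testing*. An assigner with no fixed rule leaves room for discretion in that setting. The primary outcome, peak VO2, comes from a symptom-limited treadmill test, and the text states a blinded reader for the CT images but not for this test.

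For the supplement, the two sections differ on whether the allocation is matched and randomised. That needs resolving whatever matching is taken to mean.

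**Working it through.** **Inputs from the protocol.** 60 subjects, 30 per group; four balancing factors; about 15 entrants a year; difference 17%, SD 20%, 23 completers per group, 80% power, two-sided 0.05; 20% dropout.

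**Assumed, because the protocol does not say.** Two or three levels per factor, equally likely and independent; permuted blocks of 4; minimisation that follows the balancing arm with probability 0.8.

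**1. The plan's own figure.** Standardised effect 17/20 = 0.85. The exact two-sample t-test needs 22.73, so 23 per group, with power 0.805. Enrolment: 23/0.8 = 28.75, so 29; the plan's 30 covers it. No stated figure is in dispute.

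**2. Size of the strata.**
- Two levels: 2^4 = 16 strata; 60/16 = 3.75 subjects each, fewer than one block of 4.
- Three levels: 3^4 = 81 strata; 60/81 = 0.74 each. Expected empty strata 81 × (80/81)^60 ≈ 38; expected strata with one subject 60 × (80/81)^59 ≈ 29.

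**3. Balance achieved.** Simulated sequential entry of 60 subjects, 3,000 to 5,000 trials per run. Imbalance per level is the absolute difference between arms in the number of subjects at a factor level, averaged over all levels. Ranges show the spread between independent runs.

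| Method | Imbalance per level, 2 levels | Imbalance per level, 3 levels | Mean arm-size difference, 2 levels |
|---|---|---|---|
| Simple randomisation | 4.3 | 3.5–3.6 | 6.1 |
| Stratified blocks of 4 | 2.0–2.1 | 3.1 | 2.9 |
| Minimisation, 80% | 1.3 | 1.4 | 0.9 |

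A factor level holds about 30 subjects with two levels and 20 with three. At three levels, four-factor stratification does little better than no balancing.

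**4. Literal pairing.** At 15 a year, the mean time to the next entrant in the same stratum is 16/15 = 1.07 years (about 55 weeks) with 16 strata and 81/15 = 5.4 years with 81. This assumes open-ended accrual. Within a 60-subject, 4-year trial with 16 strata, subjects who do find a partner wait a mean of 39 weeks, and about 8 of 60 never find one.

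**5. Power.** A 27 against 33 split at effect 0.85 has power 0.896, compared with 0.899 for 30/30. After 20% dropout (about 22 against 26) power is 0.819, still above the planned 80%.

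**6. Supplement.** Age and BMI are known from baseline, 12 weeks before this assignment. At 7.5 entrants per arm per year, 7.5 × 12/52 = 1.73 other same-arm subjects enter in any 12 weeks; the Poisson chance of at least one is 1 − exp(−1.73) = 82%.

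**The case against.** A reader might infer that the protocol describes three incompatible schemes. It does not. The study population section joins matching and stratification in one sentence, Group Assignment repeats the same four factors and states random assignment, and the protein-intake sentence enlarges on one of those factors with a group-level aim. The unpaired t-test fits that reading.

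A reader might also infer that matching cannot be carried out. That holds only for one-to-one pairs, which no section requires. Stratified blocks and minimisation both work with sequential entry.

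Nor does the text say that arms are chosen by judgement. It specifies an independent third party and random assignment after baseline. The missing rule permits discretion without describing it, and a predictable next assignment would require recruiters to know the pairings.

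For the supplement, one might argue that nobody can be matched because the acute study follows "two to three days after completing the primary 12-week study". But balancing can use earlier finishers and subjects still in follow-up, so another finisher within those days is not needed.

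Finally, uneven arm sizes cost almost no power, the balance figures rest on assumed factor levels, and the letter from the assigner cited under Group Assignment was not available and may say more.

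All of this stands. It does not supply an algorithm, make four-factor stratification adequate for 60 subjects, or reconcile the two supplement descriptions.

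**Conclusion.** The concern holds as one of under-specification and poor fit; it is not a contradiction or an impossibility. The main-allocation wording can be read as group-level balancing, but it cannot be executed as it stands, and the one method it names is thin for this trial. Using stratified blocks of 4 in place of minimisation leaves per-level imbalance at about 2 against 1.3 (two levels) or 3.1 against 1.4 (three levels), given equal, independent levels. Real factors will be uneven and correlated, so these figures are illustrative.

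There is no material loss of power. The reasons to act are better covariate balance and removal of discretion from a comparison that subjects cannot be blinded to. Nothing in the documents shows that selection bias will occur. The supplement discrepancy is a matter of consistency; because that treatment is blinded, bias is a smaller worry there.

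This should be corrected before enrolment. It does not invalidate the design.

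**What to change.** - **Main allocation.** Replace the wording in the study population section, Group Assignment and Dietary Control with one concealed, computer-run procedure that leaves no discretion. Either minimise on age, BMI, MHD duration and protein intake with a random element (for example 80%), or use permuted blocks stratified on only one or two of these with stated cut-points. The existing third party runs it once baseline testing is complete and then releases the arm.
- **Analysis.** Include the balancing factors in the primary model. State that the four-predictor limit in the Statistical analysis plan does not apply to it, since arm plus four factors makes five terms.
- **Whey/placebo.** Make Group Assignment and the Aim 2 section agree: a concealed permuted-block list, prepared in advance and stratified by training arm.

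**Cost.** Protocol wording and a free minimisation program. Exact balance is not guaranteed, and explicit age and BMI matching in the sub-study is given up. Four factors entered as continuous terms use four degrees of freedom: with 46 completers, 44 falls to 40.

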A. Specific Aim 1 is designed to develop an effective, safe, low-cost aerobic and resistance exercise regimen. Because of the focus on improving cardiopulmonary function as well as muscle function and mass, both resistance and aerobic exercise will be components of the rehabilitation program. The program is modeled on a successful combined in-home/in-center study program administered by [name] at the VAPAHCS rehabilitation center for patients with cardiovascular disease with a mean age of 72 years (87). In general, exercise rehabilitation is highly effective in patients with cardiovascular disease (76), including the elderly (77; 78), and is associated with improved survival rates (76; 77; 79). Subjects randomized to the exercise group will undergo 12 weeks of exercise, including a 2-week ramp-up period conducted at the VAPAHCS rehabilitation facility. Subjects will be required to attend the facility twice a week on non-dialysis days during the initial 2 weeks of the study. These sessions will consist of 45-60 min of supervised exercise that combines aerobic and resistance training, including warm-up and cool-down. Throughout the study, subjects will be asked to perform 45 minutes of unsupervised aerobic exercise of their choice (such as walking) on non-dialysis days. Following the initial 2-week supervised period, subjects will be instructed to exercise on their own, and surveillance methods will be employed as previously described (87; 93) and outlined below. Following the 12-week study period, all subjects will undergo muscle biopsies. The following end-points will be measured at baseline and after the 12 week study period:

Primary Endpoint. Peak VO₂ is the primary outcome measure and is the gold standard for cardiopulmonary fitness. It incorporates elements of cardiac, pulmonary and muscle function known to improve with exercise.

Secondary Endpoints. These include lower and upper body strength, body composition, thigh muscle mass, muscle biopsy for protein signaling, quantitative muscle morphology and gene expression, daily activities, QOL, laboratory measures of cardiovascular risk factors, nutritional and inflammatory parameters as detailed below.

Together, these measures should allow us to determine whether the home-based exercise regimen is effective in counteracting loss of muscle function and mass common in elderly MHD patients, along with reducing cardiovascular risk.

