(c) **Thigh muscle mass and fat composition** by computerized tomography (CT). Mid-thigh CT of the non-dominant limb will be performed a day after MHD, with subjects in the supine position with the thigh muscle relaxed. Axial CTs will be obtained at the midpoint between the trochanter of the femur and the superior border of the patella, using slice thickness of 2.5 mm. The radiographic film will be digitally scanned for analysis with a personal computer. The analyses will be performed by [name] (Co-Investigator), who has extensive experience analyzing CT images in patients with CKD. He will be blinded to study group when processing the images. Thigh muscle cross sectional area (a measure of muscle mass) and interstitial adipose tissue embedded in muscle (reflects muscle quality) will be measured and computed. Measurements of mid-thigh subcutaneous and total fat will also be obtained.

(4) Muscle biopsy measurements:

(a) **Biopsy procedure.** Vastus lateralis muscle will be biopsied under local anesthesia and sterile conditions with a Bergstrom needle. This procedure will be performed by [name] (Co-PI), who has extensive experience in this area. A ~150 mg sample will be obtained by applying suction to the needle at the time of biopsy as described previously (104), trimmed of fat and connective tissue and bisected. One part will be frozen at -70°C, and the remainder will be mounted in embedding medium and frozen. Biopsies will be taken at the beginning and end of the 12 week study period as detailed below.

(5) Biochemical tests:

(a) **Nutritional parameters:** Serum albumin, pre-albumin and glucose will be measured in the VAPAHCs clinical lab. Serum IGF-I and IGF binding proteins (IGFBP1, 2, 3 and 5) will be measured by ELISA and Western ligand blots as previously described in our laboratory at 0 and 12 weeks (105).

(b) **Insulin sensitivity from fasting serum glucose and insulin levels at 0, 6 and 12 weeks:**

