Primary endpoint, Specific Aim 1. For this analysis we have used data from a recent 12-week study by Storer et al (36) on the effects of endurance exercise versus no exercise (usual care) on cardiorespiratory and skeletal muscle function in MHD patients. Change from baseline for peak VO₂ was 22% (an increase) in the exercise group and 6% (a decrease) in the usual care group. These findings are consistent with an average increase from baseline of 17% in MHD patients participating in exercise-based rehabilitation programs reported in the literature (14). Similarly, our primary outcome will be comparison of the change in peak VO₂ for patients randomized to exercise vs. usual care. To calculate the desired sample size we used a two group t-test of equal means and calculated the per group sample size (East 5, Cytel Inc, copyright 2007). Given the desired values for the standardized effect size (the absolute value of the difference in group mean changes divided by the common standard deviation) and overall level of significance and power of the test, the required sample was calculated. To detect a difference in group mean changes of 17% in peak VO₂ for exercise vs. usual care, given a common standard deviation of 20% (based on Storer et al (36), using a standardized effect size of 0.85), 23 subjects/group would be required to complete the study to achieve statistical power of 80% with a two-sided test of significance at the 0.05 level. Appendix VII shows how the required sample size varies by the standardized effect size for power of 0.80 (solid curve) and 0.85 (dashed curve). Appendix VIII provides curves showing how the power varies by the standardized effect size for a per group sample size of 23 (solid curve) and 26 (dashed curve). For example, a per group sample of 23 provides power of about 0.17 and 0.38 to detect a small (0.3) and medium (0.5) standardized effect size, respectively. To allow for a 20% dropout rate we plan to enroll 30 subjects per group, or a total of 60. The 20% dropout rate is based on the PI's experience (87), and other similar research studies.

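### Thigh CT is to be analysed from scanned film with no tissue-separation rule or calibration between visits, which may cost precision in secondary outcomes, chiefly embedded fat

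*Combined protocol and SAP*

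**What the plan says.** Item (3)(c) of the measurement section describes one mid-thigh axial CT of the non-dominant limb, "using slice thickness of 2.5 mm", taken the day after dialysis. The images then pass through film: "The radiographic film will be digitally scanned for analysis with a personal computer".

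Several quantities come from these images. One is thigh muscle cross-sectional area, which the item treats as its measure of muscle mass. Another is fat within the muscle: "interstitial adipose tissue embedded in muscle (reflects muscle quality) will be measured and computed". The item adds "Measurements of mid-thigh subcutaneous and total fat will also be obtained". The reader is an experienced co-investigator, and "He will be blinded to study group when processing the images".

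The item gives no density limits, outlining rule, display window, film calibration, software or repeat-reading check. It does not mention the scanner's own digital data, and no other section replaces the film step.

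The paragraph on secondary endpoints under Specific Aim 1 lists the outcome: "These include lower and upper body strength, body composition, thigh muscle mass". The statistical analysis plan also names "change in muscle strength, and change in muscle mass" among the predictors in the regression for change in peak VO2. It does not say whether that muscle mass is taken from CT or from DEXA.

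**The concern.** A CT scan leaves the machine as a digital map of tissue density. That is general knowledge about CT and is not in the plan. Printing the map on film and scanning it back turns density into grey level, which also depends on how the film was printed and how the scanner was set. Nothing in item (3)(c) holds those settings constant between a subject's two films.

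If tissue is classified by brightness, a difference in grey scale between the baseline and week-12 films would appear as a change in fat or muscle that did not occur. Embedded fat is the most exposed quantity. It is small and interspersed in muscle, so many of its pixels may lie near the boundary between the two tissues.

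Precision in the CT outcomes is at stake. They are secondary, but they bear on Specific Aim 1, which is to counteract loss of muscle mass, and the study plans on only 23 completers per group. If the muscle-mass predictor in the peak VO2 regression is taken from CT, random error in it would tend to pull its coefficient towards zero.

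**Working it through.** The documents give no effect size, standard deviation or reliability for any CT outcome, so there is no figure of the plan to reproduce here. Both calculations below are illustrations.

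**1. Effect of a grey-scale shift on measured areas.** All inputs are assumed: muscle density 50, fat density -90, cutoff -30, pixel noise (SD) 12, 6% pure fat pixels, and 10% mixed pixels spread evenly between -90 and 50. The remaining 84% are pure muscle.

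- Pure fat lies (-30 + 90)/12 = 5 SD from the cutoff and pure muscle (50 + 30)/12 = 6.7 SD. Pure pixels are therefore almost never misclassified.
- Mixed pixels called fat with no shift: 10% × 60/140 = 4.29%.
- Fat area: 6% + 4.29% = 10.29%. Muscle area: 100% - 10.29% = 89.71%.
- A shift of s units moves 10% × s/140 of all pixels across the cutoff.

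| Shift s | Pixels moved | Change in fat area | Change in muscle area |
|---|---|---|---|
| 5 | 0.357% | 0.357/10.29 = 3.5% | 0.357/89.71 = 0.4% |
| 10 | 0.714% | 0.714/10.29 = 6.9% | 0.714/89.71 = 0.8% |
| 20 | 1.429% | 1.429/10.29 = 13.9% | 1.429/89.71 = 1.6% |

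The sign follows the direction of the shift. The result depends on the mixed-pixel share. With 5% to 15% mixed pixels, the fat change is about 2-4%, 4-9% and 9-17% at the three shifts. With none, it is 0.00%, 0.00% and 0.04%.

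**2. What such error would do to a comparison of change scores.** A shift between visits that is the same for everyone largely cancels in the difference between groups. Only shifts that vary between subjects add noise. Let R be the reliability of the change score, meaning the share of its variance that is not measurement error. Then the observed standardized effect = true standardized effect × √R. For a two-sample t-test with 23 per group and two-sided alpha 0.05:

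| Assumed R | Power, true effect 0.8 | Power, true effect 0.5 |
|---|---|---|
| 1.00 | 0.756 | 0.382 |
| 0.95 | 0.734 | 0.366 |
| 0.90 | 0.711 | 0.350 |
| 0.80 | 0.660 | 0.317 |
| 0.70 | 0.603 | 0.284 |

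For example, 0.8 × √0.80 = 0.716, which gives power 0.660. The documents do not say where in this range scanned film would fall.

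**3. The primary endpoint.** The sample size rests on peak VO2 alone: a 17-point difference, "given a common standard deviation of 20" per cent, so 17/20 = 0.85. The t-test then needs 22.7, rounded up to 23 per group, with power 0.805 at 23. This agrees with the plan, and no CT quantity enters it.

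**The case against.** The strongest objection is that the mechanism is not in the documents. Item (3)(c) does not say that muscle and fat are separated by a density cutoff. Outlining by hand, or segmenting on relative grey level within each image, fits the text equally well, and a uniform grey shift need not then mimic a change. This stands. The grey-scale mechanism is an inference, and the missing separation rule is itself part of the point.

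Next, the illustrated size comes from assumed inputs. Without mixed pixels the effect disappears, and muscle area, the CT outcome that corresponds to the listed thigh muscle mass, moves by less than 2% even at the largest shift. This also stands. The figures show what could happen and estimate nothing about this trial.

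A reader might also infer that the treatment comparison is biased. The documents do not support that: the reader is blinded, and both groups go through the same procedure. Bias would need film or scanner settings that differ by group, and nothing suggests this. Nor can a reader infer that the main result is at risk, because peak VO2 is measured without CT. Whole-body DEXA, done in duplicate, also provides a second measure of lean mass.

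The objection does not remove the step itself. The plan prescribes a conversion and describes no control over it. Recruitment is planned at about 15 subjects a year over four years, so films would be made on many different dates. Any shift in settings could therefore differ between subjects and would not all cancel.

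**Conclusion.** The point holds as a minor one. The plan specifies analysis from scanned film, with no tissue-separation rule and no calibration between visits. If CT data are available in digital form, this is an avoidable source of error. It may affect embedded fat most and muscle area less. It may also affect the other fat areas read from the same images, and the muscle-mass predictor if that is based on CT.

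The expected harm is lost precision in secondary outcomes, and its size is unknown. The film error, the mixed-pixel share and the reliability of the change score are all assumed in the figures above. The primary comparison and the sample size are not touched. The case for changing the plan rests on how little the change costs, not on a demonstrated loss.

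**What to change.** Replace the film sentence in item (3)(c) with wording such as:

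> Native digital CT data will be exported and analysed with the same prespecified density limits for muscle and for fat at baseline and week 12, by the reader blinded to study group.

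The limits should be written into the plan before any image is read. The statistical analysis plan should also say whether the muscle-mass predictor comes from CT or DEXA.

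This needs no additional scan, radiation, visit or reader, and it removes a processing step. The small downside is that it assumes the image files are retained and exportable and that the reader's software accepts them; the documents do not say. If the files are not available, scan all films with fixed print and scanner settings, calibrate each film to a common reference, and state the separation rule. That fallback costs some extra technical work.
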